4.1 Study Outcome Measures

4.1.1 Primary Endpoint:

The primary endpoint of this study is successful surgery. Successful surgery (defined as one where the device(s) stays in place and can be removed successfully during surgery) when this device(s) is placed 31 - 365 days prior to surgery. Unsuccessful surgery is defined as one where the device(s) does not stay in place and/or cannot be removed successfully during surgery) when this device is placed 31 - 365 days prior to surgery.

4.1.2 Secondary Endpoints:

- Number of days prior to surgery (31 - 365) that the SCOUT device(s) is placed by the radiologist to localize the target breast / axillary tissue.
- Success rate of device(s) placement by radiologist (within 1 cm of the center of the target tissue).
- Success rate of SCOUT localization procedure(s) stability. The SCOUT should not migrate more than 5 mm between day 0 - 365 days pre-surgery. This is measured on routine mammogram and/or ultrasound.
- Rate of device(s) related complications.

5. STUDY ENROLLMENT AND WITHDRAWAL:

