6.2 Study Procedural Intervention(s) Description

6.2.1 Placement of SCOUT Device

Investigator will read over the informed consent (English or Spanish) with potential participants and ensure that they understand the study.

All participants will be given a copy of the informed consent document for their own

reference. Possible participants will be given as much time as is necessary to make an informed decision about whether to take part in the study. The informed consent document reminds them to take their time to make their decision and to discuss the decision with their friends, family and health care team. The study physician will allow the patient to ask as many questions as they want about the process before making an informed decision as whether to take part in the study. Family members will also be encouraged to ask questions and remain involved in the subject's medical care.

Neoadjuvant treatment will be determined by experienced medical oncologist. The breast radiologists are experienced with the device placement and verification techniques (standard of care). The study device(s) will be inserted 31 - 365 days prior to surgery with standard of care technique: image-guidance, local anesthetic, and 16-g needle used to percutaneously deploy the SCOUT device at the target lesion(s). Standard of care post-procedure image verification, audio verification, and skin marking will be performed. SCOUT position will be measured relative to the center of the target lesion(s) will be consistently measured on all breast imaging mammogram/ ultrasound images until surgical excision is confirmed. These measurement will determine whether or not migration > 5 mm occurs in days 0 - 365 days prior to surgery.

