Up to 30 days prior to surgery, the standard of care device image verification and skin marking will be performed (at no charge to patient). This visit is performed as standard of care visit, usually within 7 days pre-operatively, and is coordinated with patient's other routine appointments in the same building, such as pre-admission testing. If the SCOUT device(s) is not verified in accurate and stable position (within 5 mm of initial placement as measured on mammogram and/or ultrasound imaging), the surgeon will be notified to determine whether a second localization device or wire placement will be needed. If requested, the placement of a second device using Radiology standard of care technique will be arranged at no expense to the patient up to 30 days prior to surgery.

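### The plan does not say which image decides migration; if any routine image over 5 mm counts, reading error alone raises the migration rate as images accumulate

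*Combined protocol and SAP*

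**What the plan says.** The secondary stability endpoint in section 4.1.2 is: "The SCOUT should not migrate more than 5 mm between day 0 - 365 days pre-surgery". On the source of the data it adds: "This is measured on routine mammogram and/or ultrasound". Section 6.2.1 says that position is "consistently measured on all breast imaging mammogram/ ultrasound images until surgical excision is confirmed", and continues: "These measurement will determine whether or not migration > 5 mm occurs in days 0 - 365 days prior to surgery".

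Further on, section 6.2.1 applies the same limit at one pre-operative check, up to 30 days before surgery, where the device should be "within 5 mm of initial placement as measured on mammogram and/or ultrasound imaging". Section 7.3 records that check at Visit 2 as a recheck on the Device Placement Form.

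The reference point differs between the two parts of 6.2.1: the centre of the target lesion in the first, initial placement in the second. Dwell is a separate secondary endpoint: "Number of days prior to surgery (31 - 365) that the SCOUT device(s) is placed by the radiologist". Section 9.2 plans simple statistics for each endpoint. No section schedules interim imaging, names the image that decides migration, or asks for a second reading.

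**The concern.** The decision is tied to the whole set of readings over an interval and asks whether migration occurs in it. The natural reading is that one reading over 5 mm is enough. Under that rule each further reading of a motionless device can only raise its chance of being called migrated, and the number of readings is whatever routine care produces.

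The direct consequence is a migration rate that mixes movement, reading error and intensity of imaging. With 25 to 35 subjects, one or two false crossings change the reported rate visibly. The error counts against the device.

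**Working it through.** **Inputs from the documents.** The threshold is 5 mm (4.1.2, 6.2.1). Readings are taken on all routine mammogram and ultrasound images (6.2.1). Dwell is 31 to 365 days (4.1.2). There are 25 to 35 subjects (9.1). The plan gives no migration rate or reading error to reproduce.

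**Assumptions, not in the documents.** The device does not move. Each reading has independent normal error with SD s. Each of k follow-up readings is compared with one baseline reading. Any difference over 5 mm counts. There is one device per subject.

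**One image.** The difference of two readings has SD s√2, so P₁ = 2[1 − Φ(5/(s√2))].

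- s = 1.0 mm: 5/1.414 = 3.536, P₁ = 0.04%
- s = 1.5 mm: 5/2.121 = 2.357, P₁ = 1.84%
- s = 2.0 mm: 5/2.828 = 1.768, P₁ = 7.71%

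**Any of k images.** The readings share the baseline error, so P_k = 1 − ∫ φ(z)[Φ(5/s + z) − Φ(−5/s + z)]^k dz. Numerical integration agrees with simulation:

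| s (mm) | k = 1 | k = 3 | k = 4 | k = 6 |
|---|---|---|---|---|
| 1.0 | 0.04% | 0.12% | 0.16% | 0.23% |
| 1.5 | 1.8% | 4.9% | 6.2% | 8.6% |
| 2.0 | 7.7% | 18.7% | 22.9% | 29.9% |

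**Excess due to repeated images, k = 4 against k = 1.**

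- s = 2.0 mm: 22.9% − 7.7% = 15.2%, or 0.152 × 25 = 3.8 and 0.152 × 35 = 5.3 devices
- s = 1.5 mm: 6.2% − 1.8% = 4.4%, or 1.1 and 1.5 devices
- s = 1.0 mm: about 0.1%, or fewer than 0.1 devices

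**Sensitivity to the error model.** If all readings of a device, baseline included, have error correlation ρ, s is replaced by s√(1 − ρ). At s = 2 mm and ρ = 0.5 this is 1.41 mm, and the figures fall to 1.2% for one image and 4.3% for four. If displacement is a two-dimensional distance with error SD 1.5 mm on each axis, they rise to 6.2% and 19.3%.

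**Dwell.** This step needs a further assumption: one image per 90 days plus the pre-operative image, with dwell uniform on 31 to 365 days. Split at 198 days, false migration for shorter versus longer dwell is 3.1% versus 5.7% at s = 1.5 mm and 12.1% versus 21.2% at s = 2 mm. Scoring the pre-operative image alone at s = 2 mm gives 7.6% versus 7.8%, so the gradient disappears.

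**The case against.** The best defence is that the plan can be read as a two-point comparison. Section 7.3 captures position again only at the pre-operative recheck. Section 10 lists no form for interim imaging, and its image list contains no interim response images. Section 6.2.1 itself applies the 5 mm limit at the recheck against initial placement. The interval in 4.1.2 also fits a start-to-end comparison. This stands as far as it goes: the any-image rule is an inference. But the sentence that says how migration is determined rests on readings from all images, so the two parts of 6.2.1 still need to be reconciled.

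Three stronger readings are tempting, and the documents do not support them.

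- A reader might infer that the plan creates a false link between dwell and migration. No section says that image count rises with dwell, and no analysis relating the two is planned. Even in an unplanned comparison at n = 35 and s = 2 mm, under the image schedule assumed above, a nominally significant association appears in about 6% of simulated trials (Fisher's test on split dwell) or 12% (rank correlation), against 1% and 3% with the pre-operative image alone.
- A reader might infer that false crossings become failed surgeries. The primary endpoint requires the device to remain in position but does not say that these readings decide it.
- A reader might quote the gross count at s = 2 mm and four images, about 6 of 25 or 8 of 35. Some 2 or 3 of those would be miscalled from a single image, and a single-comparison rule leaves them.

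**Conclusion.** The point holds in a conditional form. If any image over 5 mm counts, the secondary migration rate rises with the number of images even when nothing moves. The effect is negligible at a reading SD of 1 mm and material from about 1.5 to 2 mm, where the excess from four images rather than one is about 1 to 4 of 25 devices, or 2 to 5 of 35. These sizes rest on an assumed SD, an assumed image count and independent errors; correlated errors would reduce them.

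A comparison of migration by dwell would be biased only if someone made one and longer dwell brought more images. The primary endpoint is touched only if the same readings judge it. Naming one deciding comparison is nevertheless a better rule than scoring all images, and it is cheap.

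**What to change.** In sections 4.1.2 and 6.2.1, and in the matching line of the Protocol Summary, state that stability is scored once per device, as the post-placement image against the last pre-operative image (the Visit 2 recheck). Add the following:

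- One reference point, the same for both images. Section 2.2 notes that the target may disappear or be poorly seen after treatment, so the plan should say how the point is found at the recheck.
- The same modality for both images where possible.
- Devices without a recheck image are reported as not evaluable. Section 10 lists verification imaging only if available.
- Intermediate readings are listed descriptively, and the number of images per device is reported beside the rate.

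If an any-time rule is kept, count a crossing only when the next image confirms it, and say how a crossing on the last image is scored. In simulation at s = 2 mm and four images this lowers false calls from 22.9% to 3.8%, but the result still depends on the number of images.

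The cost is a few sentences and no new imaging. A transient excursion would be listed rather than counted, and single-reading error remains (7.7% at s = 2 mm). The clinical handling of a device that is not verified at the recheck is unchanged.

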6.2.2 SCOUT Device Localization

The investigator surgeons are experienced with the device and techniques. The sterile PROBE is used during the procedure to provide continuous guidance for the excision of the device and target tissue.

Standard of care specimen radiograph will be reviewed by the radiologist to verify that the device and target lesion have been obtained. These results are communicated to the surgeon in a time-sensitive manner.

7. STUDY SCHEDULE:

7.1 Screening

- Investigator identifies patients at routine initial treatment planning consultation who require neo-adjuvant therapy.
- Investigator and/or research nurse reviews medical history to determine eligibility

based on inclusion/exclusion criteria.

7.2 Enrollment/Baseline (Study Visit 1 - 31-365 days prior to surgery)

- Patient has SAVI SCOUT LOCALIZATION by Radiologist at any time prior to neoadjuvant treatment SAVI SCOUT placed anytime FDA clearance 10/31/17
- Verify inclusion/exclusion criteria.
- Surgeon and/or MCI research nurse/Investigator
 - complete the **Patient Inclusion/Exclusion Eligibility Enrollment Form**.
 - obtain **consent** from subject on **Informed Consent Form**: Before or after SAVI SCOUT LOCALIZATION and PRIOR TO NACT
 - complete **the Documentation of Consenting Process Form**
- **Research Radiologist**
 - Verifies inclusion/exclusion criteria and Assigns Study ID
 - Completes Device(s) Placement Form
 - *Sends Copy of Consent and Study ID sent to OHR for tracking.*

Sometimes, additional studies ordered by Med-Onc can impact surgical plan.

7.3 Device Placement and Post-Implant Verification (Study Visit 2, Day 0-30 days prior to surgery)

**Breast Radiologist completed standard of care pre-operative skin marking*

Research Radiologist

Completes the Device Placement Form [Device Placement Recheck]] on standard of care imaging and performs audio verification and repeat skin marking if requested as standard of care by surgeon.

If not verified, the surgeon must be notified to determine whether the patient must be scheduled for a second localization procedure 0 - 365 days prior to surgery.

7.4 Surgical Excision of Device and Lesion (Visit 3, Operative Day 0)

Research Surgeon

Performs Excision (standard of care)

Completes **Device Surgical Excision Form**

7.5 Study Completion and Unanticipated Device Adverse Event(s) Form (Operative Day 0 + 30 days)

Research Radiologist

Completes **Study Completion Form**

Completes **UADE Form** (as necessary).

**Note distinction of Breast Radiologist (standard of care SCOUT) vs. Research Radiologist (who Completes Forms)*

8. ASSESSMENT OF SAFETY:

8.1 Specification of Safety Parameters

8.1.1 Unanticipated Adverse Device Events

In this study the adverse events from underlying diseases and adverse events related to neoadjuvant treatments will not be collected.

Serious (SADE) adverse device effect or UADE involving risk to subjects or others will be reported to the IRB if the events meets all of the following criteria:

- unexpected in terms of nature, severity, or frequency given: a.) the research procedures that are described in the protocol-related documents, such as the IRB-approved research protocol and informed consent document; and b.) the characteristics of the subject population being studied.
- related or possibly related to participation in the research (“possibly related” means there is a reasonable possibility that the incident, experience, or outcome may have been caused by the procedures involved in the research).
- suggests that the research places subjects or others at a greater risk of harm (including physical, psychological, economic, or social harm) than was previously known or recognized.

8.1.2 Adverse Events

An adverse event is any untoward or unfavorable medical occurrence in a human subject, including any abnormal sign (for example, abnormal physical exam or laboratory finding), symptom, or disease, temporally associated with the subject’s participation in the research, whether or not considered related to the subject’s participation in the research.

8.1.3 Serious Adverse Events

A serious adverse event (SAE) is one that meets one or more of the following criteria:

- Results in death.
- Is life-threatening (places the subject at immediate risk of death from the event as it occurred).
- Results in inpatient hospitalization or prolongation of existing hospitalization.
- Results in a persistent or significant disability or incapacity.
- Results in a congenital anomaly or birth defect.
- An important medical event that may not result in death, be life threatening, or require

hospitalization may be considered an SAE when, based upon appropriate medical judgment, the event may jeopardize the subject and may require medical or surgical intervention to prevent one of the outcomes listed in this definition.

8.1.4 Adverse Device Effects

Adverse Device Effect is any Adverse Event related to the investigational device. This definition includes AEs resulting from deployment, implantation, operation, or any malfunction of the investigational medical device. Adverse Device Effects will be recorded by the investigator in Case Report Forms. They will be carefully monitored during the entire study.

8.1.5 Unanticipated Adverse Device Effect (UADE)

UADE is any serious adverse effect on health or safety or life-threatening problem or death caused by, or associated with, a device, if that effect, problem, or death was not previously identified in nature, severity, or degree of incidence in the investigational plan, or any other unanticipated serious problem associated with a device that relates to the rights, safety, or welfare of subjects.

Only unanticipated problems related to the deployment, implantation, and/or function of the SAVI SCOUT will be reported to the IRB/Sponsor. Potential unanticipated device effects include:

- Pain at the SAVI insertion site(s)
- Infection at the SAVI insertion site(s)
- Bleeding at the SAVI insertion site(s)
- Nonfunction of the SAVI
- Unexpected tissue reaction response at SAVI insertion site(s)
- Unexpected limitation of diagnostic quality on routine standard of care imaging

UADE must be reported as soon as possible, but no later than 10 working days after the investigator first learns of the event. If a determination has been made that a UADE presents an unreasonable risk to subjects, the investigation will be terminated no more than 5 days after making the determination and no more than 15 days after receiving notice of the event.

Device deficiencies (including but not limited to failures, malfunctions, and product nonconformities) will be reported, but will be documented and reported to the sponsor. These will not be considered adverse events. If it is possible to return the device, the device will be returned to Cianna Medical, Inc. for evaluation.

Serious Adverse Events including serious adverse device effects and UADEs will be captured throughout the study. Underlying diseases are not reported as AEs and anticipated adverse events related to the neoadjuvant treatment will not be captured.

Serious adverse events from chemotherapy and fertility preservation are ANTICIPATED

and well-documented in the consent form for Chemotherapy and the consent form for Fertility Preservation. Since these SAEs are well-known and considered unrelated to SAVI SCOUT device placement in the breast and/or axilla, the following SAEs will not be reported to the IRB:

CHEMOTHERAPY

Anticipated SAEs from chemotherapy or underlying disease are common and include, but are not limited to:

- Dehydration
- Nausea
- Vomiting
- Diarrhea
- Constipation
- Electrolyte imbalance
- Dizziness
- Loss of appetite
- Weight loss
- Palpitations
- Cardiac arrhythmia
- Heart failure
- Blood transfusions
- Fatigue
- Anxiety
- Hair loss
- Hearing loss
- Balance problems
- Loss of eye sight
- Mouth sores
- Unusual taste
- Sore throat
- Lung damage
- Problems breathing
- Burning when passing urine
- Blood in the urine
- Elevated blood sugar
- Kidney damage
- Renal failure
- Loss of fertility
- Pain in jaw
- Weak muscles
- Change in mood (angry, depressed)
- Altered mental status and confusion

- Nerve damage (lose ability to move parts or all of body, tingling in extremities)
- Low white or red blood cell count with increased risk of fatigue
- Infection
- Low platelet count with increased risk of bruising and bleeding
- Cardiac toxicity
- Small risk of development of leukemia and shortness of breath
- Veins at chemotherapy infusion site may harden, become painful, or develop sores and the skin tissue in the surround area may be destroyed.
- The chemotherapy treatment may cause a new cancer to form.

FERTILITY PRESERVATION

Anticipated serious adverse events from fertility preservation/egg harvesting or underlying disease are common and include but are not limited to:

- Adult and childhood cancer
- Infertility
- Infection at the medication injection site
- Pain at the medication injection site
- Infection associated with egg retrieval or embryo transfer
- Pelvic infection
- Abdominal infection
- Damage to other intra-abdominal organs during the egg retrieval
- Damage to the bowel, appendix, bladder, ureters, and ovary
- Genetic problems in children born from Intracytoplasmic Sperm Injection (ICSI)
- Birth defects
- High-order multiple gestations (triplets or greater)
- Damage to the embryo
- Cerebral palsy
- Developmental delay.
- Normal risks of subsequent pregnancy include pregnancy loss, gestational diabetes.

Ovarian Hyperstimulation Syndrome (OHSS) is a serious side effect. Symptoms can include:

- Increased ovarian size
- Nausea
- Vomiting
- Accumulation of fluid in the abdomen which could require drainage
- Breathing difficulties
- Increased concentration of red blood cells
- Kidney problems
- Liver problems
- In the most severe cases, blood clots, kidney failure, or death

Potential side effects include, but are not limited to:

- Hot flashes
- Vaginal dryness
- Bone loss
- Nausea
- Vomiting
- Fluid retention
- Muscle aches
- Headaches
- Change in Mood (Depression/Anxiety)
- Abdominal pain
- Skin reaction at the injection site
- Sleepiness
- Allergic reaction

If given by intra-muscular injection includes the additional risk of:

- Infection at the injection site
- Pain at the injection site
- Irritation at the application site

If given by transdermal route:

- Risk of stroke
- Increased moodiness
- Vaginal infection
- Diarrhea
- Rashes
- Sensitivity to the sun
- Allergic reactions
- Drowsiness
- Severe infections
- Damage to the internal organs.
- Abdominal discomfort could result in the need for hospitalizations for observation purposes
- Cysts could rupture requiring emergency surgery to stop the bleeding and could result in a need for blood transfusions and possible loss of one or both ovaries, the stimulated ovary can twist on itself, cutting off its own blood supply.
- Feelings of anxiety, depression, isolation, and helplessness are not uncommon among patients undergoing chemotherapy and/or infertility treatment.
- Strained and stressful relations with spouses, partners and other loved ones are not uncommon as treatment gets underway and progresses.

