2.1 Description of the SAVI SCOUT Breast Localization and Surgical Guidance System

The SAVI SCOUT Surgical Guidance System (SAVI SCOUT, Cianna Medical, Inc.) is an FDA cleared medical device that aids in the surgical excision of breast lesions without the use of wires or radioactive materials. The system employs nonradioactive light-activated radar SCOUT device, which is placed in breast or axillary lesions under imaging guidance up to 365 days prior to surgery, to guide the surgical excision of non-palpable lesions (Standard of Care).

The system consists of the SCOUT (device) and two major components:

1. A localization SCOUT (device) is placed, percutaneously via a 16-gauge needle at the breast/axillary lymph node lesion. The device uses light (radar) technology to activate an audio and numeric signal to aid the surgeon to locate the target tissue. The device contains nitinol wire, which is a standard medical material composed of nickel and titanium. After placement, the device is safe and visible under all standard imaging modalities (Mammogram, Ultrasound, CT, PET-CT, X-ray, and MRI).
2. A handpiece (PROBE) is used by the surgeon intra-operatively. In the operating room, the sterile PROBE is connected to the console and is placed in direct contact with the skin or within breast/axillary tissue to send /receive the audio and numeric signal to guide the surgeon.

Figure 1. SCOUT System Components

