8.3 Characteristics of an Adverse Event

8.3.1 Relationship to Study Intervention

To assess relationship of an event to study intervention, the following guidelines are used:

8.3.1.1 Related (Possible, Probable, Definite):

- The event is known to occur with the study intervention.
- There is a temporal relationship between the intervention and event onset.
- The event abates when the intervention is discontinued.
- The event reappears upon a re-challenge with the intervention.

8.3.1.2 Not Related (Unlikely, Not Related):

- There is no temporal relationship between the intervention and event onset.
- An alternate etiology has been established.

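### The exempt-SAE list in 8.1.5 has no site limit for infection and needs no prior relatedness assessment, so a device-site infection during chemotherapy could go unrecorded

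*Combined protocol and SAP*

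**What the plan says.** Section 8.1.5 sets out two lists.

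- **Device list.** It gives examples of potential unanticipated device effects. They include pain, infection, bleeding and unexpected tissue reaction at the insertion site. Unanticipated problems with the device go to the IRB and sponsor.
- **Exempt list.** It covers SAEs from chemotherapy and from fertility preservation. The rule calls these SAEs well known and "considered unrelated to SAVI SCOUT device placement in the breast and/or axilla", and then says "the following SAEs will not be reported to the IRB". The lists that follow are expressly not exhaustive. The chemotherapy list has an entry for infection with no body site, and the entry "Low platelet count with increased risk of bruising and bleeding".

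Two sentences limit recording as well as reporting. Section 8.1.1 says that "adverse events related to neoadjuvant treatments will not be collected", and 8.1.5 says anticipated events related to that treatment will not be captured. Yet 8.1.5 also says that SAEs, including serious device effects and UADEs, are captured for the whole study.

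Section 8.1.4 puts adverse device effects on the case report forms. Section 8.3.1 gives criteria for individual events: "To assess relationship of an event to study intervention, the following guidelines are used". Section 4.1.2 makes the rate of device-related complications a secondary endpoint.

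**The concern.** The device is placed before neoadjuvant treatment starts (5.2) and stays in until surgery, so device exposure and treatment exposure overlap by design. Infection is both a stated risk of the localization procedure (2.3.1) and an entry on the exempt chemotherapy list. For such an event the cause is the open question, and the plan offers a ready answer before anyone has looked at the case.

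An event attributed to treatment is not merely left out of an IRB report. Under the non-collection sentences it may not enter the study data at all, so it could not be re-adjudicated later. At stake are the device-complication rate and a safety signal. Section 2.2 ties the value of the study to good performance without device-related complications, so even a single event matters to the conclusion.

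**Working it through.** The plan gives no rate for serious infection or bleeding due to the device, so there is no figure of its own to reproduce. The check is mainly a comparison of rules.

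**Step 1. One event under each rule.** Take a serious infection at the device site in a patient whose white count is low from chemotherapy.

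| Rule | Result |
|---|---|
| 8.1.5, device list | Infection at the insertion site: a potential device effect, reportable |
| 8.1.5, exempt list | Infection, no site limit: unrelated if taken as an SAE from chemotherapy, not reported to the IRB |
| 8.1.1 and 8.1.5, non-collection | Not collected or captured if attributed to treatment |
| 8.1.5, capture of SAEs | Captured throughout the study |
| 8.1.4 | On the case report form, once judged device-related |

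The rows disagree, and no sentence ranks them.

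**Step 2. Is there an assessment before the exemption applies?** Section 8.3.1 has criteria, but no section makes them a precondition for the exemption or for non-collection, and none names who judges relatedness. One criterion for calling an event not related is that another cause has been established. The exempt list supplies such a cause in advance.

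**Step 3. Does the device list close the gap?** Not fully. A UADE must be serious and not already identified in the plan, and 2.3.1 already identifies infection and bleeding. IRB reporting under 8.1.1 requires all three of its criteria, including that the event be unexpected. The adverse-event form named in section 10 is for unanticipated device events, and 7.5 has it completed as necessary.

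**Step 4. The bleeding case.** The chemotherapy list mentions bleeding only as a risk that goes with low platelets. A bleed at the device site could be attributed that way, but the path is less direct than for infection.

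**Step 5. Scale.** Inputs: 25 to 35 subjects (9.1). Assumption: the rate is per patient.

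- Change from one lost event = 1/n: 1/25 = 4.0 points; 1/35 = 2.9 points.
- Exact (Clopper-Pearson) 95% intervals: 0/25, 0 to 13.7%; 1/25, 0.1 to 20.4%; 0/35, 0 to 10.0%; 1/35, 0.1 to 14.9%.
- Chance that at least one such event occurs = 1 − (1 − p)^n. The rate p is assumed, from 1% to 5%. For n = 25: 1 − 0.99^25 = 22% to 1 − 0.95^25 = 72%. For n = 35: 1 − 0.99^35 = 30% to 1 − 0.95^35 = 83%.

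These are chances that an event occurs. They are not chances that it is lost.

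**The case against.** The best defence is that the exemption depends on attribution. It covers SAEs from chemotherapy or fertility preservation, and a device-caused infection is not one. On this view 8.3.1 supplies the attribution step. The sentence on unrelatedness governs IRB reporting only. Device effects still go on the case report forms (8.1.4), investigators ask about events at each visit (8.2), subjects are told to report device problems (2.3.3), and 8.1.1 accepts a possible relation for its relatedness criterion.

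Much of this stands, and it rules out several stronger readings that a reader might infer:

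- **That all serious infection, bleeding and allergic reaction is declared unrelated by name.** The wording is limited to events from the two treatments, and site infection and bleeding are named as device effects.
- **That allergic reaction is a main part of the problem.** "Allergic reactions" and its singular form appear only under fertility preservation, not under chemotherapy. It is true that "The device contains nitinol wire, which is a standard medical material composed of nickel and titanium". However, known or suspected nickel allergy is an exclusion (5.3), the device list is illustrative, and a serious device-related reaction fits the general definitions in 8.1.4 and 8.1.5.
- **That one lost event outweighs the risks the protocol quotes.** The figures of less than 1% and 2 - 3% in 2.3.1 and 2.3.3 concern migration and vasovagal events, so they are not comparators.

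What the defence does not supply is the missing link. No sentence requires the 8.3.1 assessment to be done and documented before an event is set aside, and the non-collection sentences do reach recording.

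**Conclusion.** The point holds as a conflict between stated rules. The exempt list is open-ended, carries infection without a site and is not conditional on an assessment of relatedness. It conflicts with the insertion-site list, and the non-collection sentences conflict with the statement that SAEs are captured throughout. Following the text could leave a device-related infection during chemotherapy unrecorded and, less clearly, a device-site bleed attributed to low platelets. Either would lower the device-complication rate.

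The size per lost event is 4.0 points at 25 patients and 2.9 at 35, with patients as the denominator. That is the arithmetic of any small study. The documents do not show that an event will be lost, how many might be, or that the rate will in fact be biased. Loss requires misattribution, which the plan permits but does not direct. The case report forms are not in the documents and may close part of the gap. This is an inexpensive improvement worth making.

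**What to change.** Reconcile 8.1.1, 8.1.5 and 8.3.1 with three statements:

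1. The IRB exemption and the non-collection rule apply only to events assessed under 8.3.1, and documented, as not device-related.
2. Where an event fits both lists, the insertion-site list overrides the exempt list.
3. Any infection, bleeding or tissue reaction in the breast or axilla carrying the device is recorded on the case report form and assessed for relationship, whatever its suspected cause.

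The sentence on capturing SAEs and the sentence on not capturing treatment-related events should then be reworded to agree. The cost is a few sentences and a few more relatedness assessments. Treatment, visits and sample size do not change.
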